**The I-FiBH Trial: Intravenous Fluids in Benign Headaches Trial: A Randomized Single
Blinded Clinical Trial**

NCT 03185130

March 15, 2017

INTRODUCTION

Migraine headache has a 1-year period prevalence in the US of 11.7% and accounts for approximately 1.2 million migraine visits to US emergency departments per year [1,2]. There are numerous studies that discuss treatment for migraine and other benign headaches within the emergency department, however, there are very few that discuss specifically the use of intravenous fluids (IVF) for headache treatment [3]. Many of these studies look at various options for treating migraine and other benign headaches: treatment options include dopamine antagonists, opioids, non-steroid anti-inflammatory drugs (NSAIDs), triptans, anti-epileptics and ergot derivatives [2]. Comparisons have been done between many of these treatment options with dopamine antagonists appearing to be the most effective, compared to other treatments [4, 5, 6, 7]. The dopamine antagonist with the most evidence and availability for benign headaches is prochlorperazine [6, 7, 8, 9, 10, 11, 12].

Peripheral IVs and administration are common procedures and treatments within the ED. And while relatively safe, they are not without their own risks [13, 14, 15, 16]. Given that IVF administration is a common part of treatment regimen for benign headache patients in the emergency department and given the lack of randomized trials in adults, we aim to study the use of IVF on pain reduction in headache patients in the adult ED [3]. Given the specific definition of migraine headache, we have chosen to categorize our headaches as benign headaches, avoiding the difficulty of determining if a patient meets the specific criteria for migraine headache [17, 18]. There has been one randomized trial in pediatrics that shows IVF may help in patients with migraines, whereas the adult literature has no randomized control trials and a review of data shows that fluids do not help relieve pain in migraine headache patients [3, 19, 20].

We will design a single blinded randomized trial to study the effects of IVF on benign headaches. There are numerous challenges using the International Headache Society guidelines for controlled drug trials in acute migraines, including having a patient population that knows the specifics of migraine headaches and meets the exact definition. In order to facilitate obtaining the necessary number of patients we will include all benign headache patients [17,18].

METHODS

Study Design

This will be a single center, prospective, single blinded randomized controlled trial on a convenience sample of patients presenting to the adult or pediatric ED with a chief complaint of headache. Subjects will only be enrolled when a physician or research assistant who is familiar with the study protocol is available to enroll patients.

Selection of Participants

Previous data have found that patients presenting to the ED with an undifferentiated headache improve with all the above-described headache medications regardless of whether or not they meet the definition of migraine, tension headache, or another primary headache disorder [7, 8, 11]. Therefore, this study will enroll all patients between the ages of 10 and 65 who meet all of the inclusion criteria and do not meet any of the exclusion criteria, who present to the ED with a benign headache.

Inclusion Criteria

Patients who present to the ED with complaint of a headache with the following criteria:

- Age 10 to 65 years
- Temperature < 100.4° F
- Normal neurologic exam and normal mental status

Exclusion Criteria

- Pregnant.
- Meningeal signs are present
- Acute angle closure glaucoma is suspected.
- Head trauma within the previous two weeks
- Lumbar puncture within the previous two weeks
- Thunderclap onset of the headache
- Known allergy to one of the study drugs.
- History of intracranial hypertension.
- Is a prisoner
- Patient declined informed consent
- Non-English speaking patient or parent/guardian for pediatric patients
- Attending provider excludes patient
- Severe dehydration

Informed Consent

Written, informed consent will be obtained from each patient. Consent will include a discussion of the risks and benefits. In addition to parental informed consent in the pediatric population, age appropriate verbal assent will be obtained from pediatric subjects.

Risk/Benefit

The risks are the side effects associated with each drug. For prochlorperazine, this includes drowsiness, blurred vision, xerostomia, congestion, nausea, akathisia, tardive dyskinesia, NMS, and blood dyscrasias. For Benadryl include sedation, tiredness, sleepiness, dizziness, constipation, dry mouth, blurred vision, nausea, and loss of appetite. For normal saline, this

includes injection site swelling, redness, infection, venous thrombosis or phlebitis or hypervolemia. Personal benefits include intended reduction in headache symptoms and the satisfaction that the patient may be assisting investigators in determining a more effective headache treatment.

Interventions

After enrollment, each patient will be randomized either to the standard treatment arm to receive prochlorperazine 0.15 mg/kg up to 10 mg IV along with diphenhydramine 1mg/kg (up to 50 mg) IV and normal saline at 5 mL/h IV OR to the study arm to receive prochlorperazine along with diphenhydramine IV and normal saline at 20 mL/kg (up to 1000 mL) given IV over 1 hour. The diphenhydramine will be administered first, and immediately afterward the prochlorperazine will be administered. The patient will then be connected to normal saline on an IV pump and randomized to 5 cc over an hour or 20 cc/kg (maximum 1000 cc) over one hour. The IV bag and pump will be covered so that the patient will not know how much fluid they are receiving. Patients will undergo simple randomization to either the fluid bolus group or the control group. The treating physician will consult a folder that contains a list specifying the group assignment. Each row of the list corresponded to a patient, and will be covered by a small slip of opaque paper that will be removed at the time of enrolment to reveal the group assignment. This list was constructed at the beginning of the study using a random number generator by a research staff. Randomization in the pediatric ED and adult ED will be separate to ensure equal numbers of pediatric patients in both the experimental and control arms (blocking). Emergency providers will be instructed not to administer any rescue medications for at least 30 minutes.

Safety

After 30 minutes, the treating provider will be permitted to administer a “rescue medication” of their choice for further treatment. If there is an untoward event that requires the patient to know which IVF dose was administered, patient will unblinded and will not continue in the study.

Reportable Events

Anticipated side effects are those listed on the manufacturer’s package insert and are treated as routine non-urgent or non-emergent events are not reportable events.

Adverse Events are those unanticipated side effects that require interventions or anticipated side effects that do not respond to intervention.

Serious Adverse Events are those side effects that require Advanced Life Support measures to control symptoms.

AEs and SAEs will be reported to the IRB within 5 days of the event.

Methods of Measurement

Enrolled patients will fill out a brief data collection form to include age, sex, race, phone number, and baseline headache severity using a 100-mm visual analog scale (VAS). Repeat headache severity scores will be measured at 30 and 60 minutes. Time zero begins immediately after complete administration of the study drug. Nausea (with a 100 mm VAS) and vomiting will also be assessed at these time intervals. The need for rescue medications will be extracted from the patient's chart at a later time.

Trained research assistants will call the patient 24-48 hours post-discharge by phone to ask if they are currently having a headache (yes or no) and to rate their current pain (0-10). If the patient is admitted, the patient will be approached in the hospital by an investigator or research assistant for follow up.

Outcome Measures

The primary outcome measure will be the difference in pain scores between the 5 cc over an hour and 20 mg/kg (up to 1000 cc) over an hour groups measured as the absolute difference between the means at 60 min. Secondarily, we will measure the difference between the rates of decline in pain scores, rate of admission, nausea scores, rate of vomiting, rate of use of additional medications for headache, and headache resolution with telephone follow up.

Privacy and Security

In order to protect the privacy of the research subjects and to maintain the confidentiality of data, all data will be managed only by trained research assistants or investigators and will be stored in the locked Emergency Medicine research offices and electronic data will be stored on a password protected computer in the locked Emergency Medicine research office. All research assistants and investigators are HIPAA- trained, CITI trained and credentialed by UMC IRB, and oriented to the study protocol.

Data Analysis:

Assuming a SD of 22 (based on prior data from our institution), we calculated that we would need 45 patients in each group to find a clinically important difference in pain score reduction (13 mm) between groups at 60 min with at least 80% power and an alpha of 0.05.

The groups will be compared using a t -test on gender, race, and age; and a chi (with Yates correction)-squared test on severity of presenting headache, to determine if they are similar. The individual VAS measurements will be compared using a repeated measures analysis of variance (ANOVA) test.

REFERENCES

[1] R.B. Lipton, M.E. Bigal, M. Diamond, F. Freitag, M.L. Reed, W.F. Stewart, et al. Migraine prevalence, disease burden, and the need for preventive therapy. *Neurology*, 68 (2007), pp. 343–349

[2] B.W. Friedman, J. West, D.R. Vinson, M.T. Minen, A. Restivo, E.J. Gallagher. Current management of migraine in US emergency departments: an analysis of the National Hospital Ambulatory Medical Care Survey. *Cephalalgia*, 35 (2015), pp. 301–309

[8] Jones J, et al. Randomized double-blind trial of intravenous prochlorperazine for the treatment of acute headache. *JAMA*. 1989;261:1174-1176.

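### Patients are randomised to up to 1000 mL of saline in an hour, but no eligibility criterion names a condition that raises the risk of fluid overload

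*Combined protocol and SAP*

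**What the plan says.** Under Interventions, the study arm is given "normal saline at 20 mL/kg (up to 1000 mL) given IV over 1 hour"; the control arm gets 5 mL over the hour. Both arms receive the same prochlorperazine and diphenhydramine, so fluid volume is the only planned difference. Under Risk/Benefit, the listed risks of normal saline include "infection, venous thrombosis or phlebitis or hypervolemia".

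The 3 inclusion criteria cover age (10 to 65), temperature, and neurologic and mental status. The 13 exclusions include "Known allergy to one of the study drugs", history of intracranial hypertension, severe dehydration and, as an open item, "Attending provider excludes patient". Nothing states the grounds on which an attending should exclude.

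On who enrols, Study Design says: "Subjects will only be enrolled when a physician or research assistant who is familiar with the study protocol is available to enroll patients". On allocation, Interventions says: "The treating physician will consult a folder that contains a list specifying the group assignment". After entry, the Safety section provides that following an untoward event for which the fluid dose must be disclosed, the "patient will unblinded and will not continue in the study".

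**The concern.** The protocol recognises fluid overload as a hazard of the randomised treatment but has no entry criterion directed at it. A patient with heart failure, or on dialysis, passes every criterion that names a condition. That patient can then be allocated by chance to as much as a litre in one hour unless the attending thinks to intervene.

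The list does not leave all contraindications to judgment. Drug allergy, suspected angle closure glaucoma and intracranial hypertension are written out. Volume status appears in one direction only: marked dehydration is excluded, whereas poor tolerance of a fluid load is not mentioned. Because a research assistant's availability is enough for enrolment to proceed, the person screening may have nothing in the written criteria that prompts the question.

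What is at stake is patient safety. No claim is made about bias, power or adverse-event reporting.

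**Working it through.** **1. The plan's own figure.** Data Analysis gives 45 per group from SD 22 mm, difference 13 mm, 80% power and alpha 0.05. The normal approximation, two-sided, is n = 2 × (1.960 + 0.842)² × 22² / 13² ≈ 45, with power 0.800. (The exact t-test gives 46, with power 0.792 at 45.) The figure reproduces. The concern does not depend on it, except that 45 is used below as the number given the bolus.

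**2. Reading the criteria.** Each of the 3 inclusions and 13 exclusions was checked for a cardiac, renal, hepatic, fluid-restriction or overload condition. None has one. The nearest item, severe dehydration, concerns a deficit. Of the 13 exclusions, only the attending's discretion could remove a patient because of overload risk.

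**3. Dose delivered.** Volume = min(20 mL/kg × weight, 1000 mL), so the cap applies from 1000 / 20 = 50 kg.

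| Weight | Volume in 1 h | mL/kg |
|---|---|---|
| 30 kg | 600 mL | 20.0 |
| 50 kg | 1000 mL | 20.0 |
| 70 kg | 1000 mL | 14.3 |
| 100 kg | 1000 mL | 10.0 |

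**4. Chance of exposing an at-risk patient.** Two inputs are missing from the documents and are assumed here: p, the share of otherwise eligible patients at raised risk of overload, and c, the share of those whom attendings would exclude. Among enrolled patients the at-risk share is q = p(1 − c) / (1 − pc). The chance of at least one among 45 bolus patients is 1 − (1 − q)^45, and the expected number is 45q.

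| Attendings exclude (c) | p = 0.5% | p = 1% | p = 3% |
|---|---|---|---|
| 0 (worst case) | 20% (0.23) | 36% (0.45) | 75% (1.35) |
| 50% | 11% (0.11) | 20% (0.23) | 50% (0.69) |
| 90% | 2% (0.02) | 4% (0.05) | 13% (0.14) |

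Expected numbers are in brackets. As an example, p = 1% and c = 50% give q = 0.005 / 0.995 = 0.00503, and 1 − (1 − 0.00503)^45 = 0.203.

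**5. Recruitment cost of an exclusion.** If attendings currently exclude none of these patients, reaching 90 requires approaching 90 / (1 − p) = 90.5, 90.9 or 92.8. Rounded up, that is 1, 1 or 3 more.

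**The case against.** The strongest reply is that a physician check already exists. The attending's power to exclude is a listed criterion, and its open wording can cover contraindications that a fixed list would miss. The Introduction says that "IVF administration is a common part of treatment regimen for benign headache patients in the emergency department", so attendings make this judgment routinely. The treating physician also reveals the allocation, and nothing in the protocol says that assistants decide eligibility from the list alone. The dose is weight-based and capped, patients are no older than 65, pregnancy is excluded, and risks are discussed at consent. Nor is saline a special case: neuroleptic malignant syndrome and blood dyscrasias are listed as prochlorperazine risks without a matching exclusion. Finally, the exposure figures rest wholly on assumed rates, and the proposed wording still needs judgment.

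Much of this is fair. Routine practice would probably catch some of these patients, the 20% to 75% row is a worst case, and the documents do not show which row applies. What remains is that none of these features asks about overload risk before randomisation. The cap limits dose, consent informs, and withdrawal follows an event. The treating physician is not told to screen for overload, and withholding fluid once the slip is removed is not an entry screen. In routine care the clinician chooses the volume for the patient; here chance does. The prochlorperazine comparison shows that other listed risks also lack exclusions, but both arms receive that drug, whereas fluid volume is what the trial randomises.

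**Conclusion.** The concern holds. The eligibility criteria contain no named screen for a hazard that the protocol itself attributes to the randomised treatment, and at entry the only protection is discretion without stated grounds. This follows from the text with high confidence.

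Its practical size is uncertain. Under assumed at-risk shares of 0.5% to 3% and attending exclusion rates of 0 to 90%, the chance of giving the bolus to at least one at-risk patient among 45 runs from 2% to 75%. That is a chance of exposure; the documents give no basis for estimating harm. The recommendation does not rest on any one of these rates. It is a change that should be made on safety grounds, and it leaves the primary analysis and the 45 per group as they are.

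**What to change.** Add one line to Exclusion Criteria:

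> Any condition in which a rapid IV bolus of up to 1 L is contraindicated, such as heart failure, advanced renal failure or dialysis, or another fluid-restricted or volume-overloaded state.

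Keep the attending's exclusion for anything not named. Some judgment remains in the general clause, but the named conditions become a fixed item that whoever enrols checks before the allocation slip is removed.

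The cost is a short protocol amendment and one checklist line, with slightly narrower generalisability. At the assumed shares, at most 1 to 3 more patients would have to be approached to reach 90, and fewer if attendings already exclude some of them.

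### Allocation is concealed only by an opaque slip over each row of a list the treating physician consults, with no seal, custody rule or timed record to prevent or reveal an early look

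*Combined protocol and SAP*

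**What the plan says.** METHODS – Interventions describes how the sequence is made and hidden. On its origin: "This list was constructed at the beginning of the study using a random number generator by a research staff". On access: "The treating physician will consult a folder that contains a list specifying the group assignment". On concealment, each row "will be covered by a small slip of opaque paper that will be removed at the time of enrolment to reveal the group assignment". The method is given as follows: "Patients will undergo simple randomization to either the fluid bolus group or the control group". The two departments are handled apart: "Randomization in the pediatric ED and adult ED will be separate to ensure equal numbers of pediatric patients in both the experimental and control arms". That implies at least two sequences, presumably one list per ED.

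On who enrols, Study Design describes a convenience sample and adds: "Subjects will only be enrolled when a physician or research assistant who is familiar with the study protocol is available to enroll patients". On who may be kept out, one listed exclusion criterion reads "Attending provider excludes patient", with no reason required.

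On timing, Interventions opens with "After enrollment, each patient will be randomized either to the standard treatment arm". It later places removal of the slip at enrolment. In between, it has both drugs given first and the patient randomized on being connected to the pump.

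The documents do not describe a seal, a custodian for the folder, a signature or time at the reveal, or a log of patients screened and excluded.

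**The concern.** Concealment protects the step before assignment: whoever decides that a patient enters must not know which arm comes next. This is separate from the single blinding of the infusion, which concerns what is known after assignment.

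Here the upcoming rows are in a folder a clinician consults, and a slip is the only barrier described. Enrolment is by convenience, a physician may enrol, and the attending provider may exclude a patient without giving a reason. If someone looked at the next row before the decision was final, a patient could be excluded or deferred because of it. The Introduction calls fluid a common part of ED headache treatment, so some clinicians may well hold a preference.

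The primary outcome under Outcome Measures is the difference between group means at 60 minutes, and no baseline adjustment is stated for it. A steered difference between the groups would enter that estimate directly. Patients left out after an early look could not be recovered by any analysis.

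**Working it through.** **1. The order of steps.** Three statements in Interventions bear on when a patient is randomized:

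- after enrolment (opening sentence);
- at enrolment, when the slip is removed (list procedure);
- after diphenhydramine and prochlorperazine, on connection to the pump (drug sequence).

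The first two can be read together as eligibility, then enrolment, then reveal. The third puts the act later. None requires the eligibility decision to be written down before the reveal, and none says that a revealed row is final.

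**2. Whether past rows help.** Under truly simple randomization earlier assignments do not predict the next, so foreknowledge requires lifting a slip. The aim of equal pediatric numbers, which the plan labels as blocking, does not fit easily with simple randomization. If small blocks were used, rows already uncovered would also help prediction.

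**3. The plan's own figure.** Data Analysis gives SD 22 mm, difference 13 mm, 80% power and alpha 0.05. With a two-sided normal approximation:

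n = 2 × (1.960 + 0.842)² × 22² / 13² = 44.96, so 45 per group.

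This reproduces the stated number. (An exact t-test gives 46, with power 0.792 at 45.) The fix does not change it.

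**4. Standard error.** SE = 22 × √(2/45) = 4.64 mm.

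**5. Assumed bias.** The documents give no steering rate, so these inputs are assumptions. Bias in one arm = fraction steered × difference in 60-minute VAS between the patients taken and those they replace; it doubles if the other arm is steered the opposite way.

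- Illustration: 0.10 × 20 = 2 mm, or 4 mm if mirrored. Against 13 mm these are 2/13 = 15% and 4/13 = 31%.
- Low end: 0.05 × 10 = 0.5 mm in one arm.
- High end: 0.15 × 20 = 3 mm, or 6 mm if mirrored.

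**6. Effect on the test.** With no true effect and bias b, the two-sided rejection rate is Φ(b/SE − 1.96) + Φ(−b/SE − 1.96). With a true 13 mm effect and bias against it, power is Φ((13 − b)/SE − 1.96).

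| Bias (mm) | False-positive rate | Power if bias opposes a 13 mm effect |
|---|---|---|
| 0 | 5.0% | 80% |
| 0.5 | 5.1% | – |
| 1 | 5.5% | – |
| 2 | 7.2% | 66% |
| 4 | 13.9% | 49% |

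A noncentral t with 88 df gives 7.1% and 13.7% at 2 and 4 mm.

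**7. A second set of assumptions.** Suppose a fraction g of rows is previewed and enrolment is then steered fully on an impression that correlates r with 60-minute pain. Expected bias = g × r × 22 × 1.60 mm. With r = 0.3 and g = 0.10, 0.25 and 0.50, the simulated bias was about 1.1, 2.6 and 5.3 mm, and the false-positive rate about 6%, 9% and 20%.

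**The case against.** The strongest reply is that the plan already sets a safe order. Only patients who meet no exclusion criterion are enrolled, attending exclusion is one of those criteria, and the slip comes off at enrolment. Lifting a slip and then excluding the patient would breach the protocol. The sequence came from a random number generator run by research staff, and the slips are opaque and cover one row each. This stands as a statement of intent. It does not answer the gap: nothing described would prevent or detect a breach, and the drug sequence blurs the order.

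The motive can also be disputed. The Introduction says reviewed adult data show no pain relief from fluid, and severe dehydration is already an exclusion. That makes a strong preference less certain, but does not rule one out. Baseline VAS is collected and presenting severity compared, which could partly reveal steering on pain. It would not show steering on factors the data form does not record, or the patients left out.

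A reader might infer more: loose slips on a single open list, kept by the treating physician in the clinical area, who can exclude patients at will and leave no trace. The documents do not support this. They do not say how the slips are attached or where the folder is kept. The physician is said to consult the folder, and that does not establish custody. Separate randomization implies at least two sequences. The attending provider who excludes may not be the treating physician who consults the folder.

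**Conclusion.** The point holds as a weakness in allocation concealment. Assignments are reachable by a clinician before enrolment is irrevocable, the eligibility decision need not be recorded first, and the point of randomization is stated inconsistently. It does not show that anyone looked ahead or that enrolment was steered, and a reader should not take it that way.

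The size is illustrative. The SD and group size are the plan's; the steering fraction and VAS difference are assumed. A difference of 20 mm is 20/22 = 0.91 of the planning SD, and the 4 mm figure also needs opposite steering in both arms. On those inputs the false-positive rate rises from 5% to about 7% (2 mm) or 14% (4 mm); at 0.5 to 1 mm it stays at 5.1% to 5.5%. The case for acting rests on the low cost of prevention and on the fact that this kind of selection cannot be undone in analysis.

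**What to change.** In METHODS – Interventions:

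- Replace the slip-covered list with sequentially numbered, opaque, sealed envelopes, one set per ED, prepared and held by research staff who do not enrol. The split between EDs is unknown, so 90 in total is too few: 2 × 90 = 180 would cover any split of 90 patients.
- Before the next envelope is opened, record on the data form, with times: consent; eligibility, including any attending exclusion and its reason; and baseline VAS. The opener signs and times the envelope.
- State one point of randomization, and reconcile the three descriptions with it.
- State that once an envelope is opened the patient counts as randomized and is kept in the analysis in the assigned group. This concerns the analysis only. It does not restrict clinical decisions to stop study treatment, and it should be worded to fit the Safety section, under which an unblinded patient does not continue.

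The cost is some preparation, a protocol paragraph, a few lines on the data form and a minute or two per enrolment. The custodian must be reachable while the trial is enrolling. The sample size is unaffected.

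### Simple randomization from separate adult and pediatric lists cannot guarantee equal numbers of children per arm, and the analysis does not say whether emergency department is a model factor

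*Combined protocol and SAP*

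**What the plan says.** In Interventions, the method of allocation is given as "Patients will undergo simple randomization to either the fluid bolus group or the control group". The source of the list is also given: "This list was constructed at the beginning of the study using a random number generator by a research staff". The same paragraph adds that "Randomization in the pediatric ED and adult ED will be separate", and gives the purpose as "to ensure equal numbers of pediatric patients in both the experimental and control arms (blocking"). No block size or other balance restriction appears anywhere in the document.

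In Outcome Measures, the primary outcome is the difference in pain score between the two fluid groups, "measured as the absolute difference between the means at 60 min". ED is not mentioned there.

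In Data Analysis, the pain scores get one sentence: "The individual VAS measurements will be compared using a repeated measures analysis of variance (ANOVA) test". It lists no factors or covariates. The sample size statement is "we would need 45 patients in each group", for a 13 mm difference with an SD of 22, at least 80% power and alpha 0.05. The planned number of children is not given.

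**The concern.** The statements on allocation do not fit together. Under simple randomization each child's assignment is an independent draw, and keeping a separate list for the pediatric ED does not change that. Equal numbers would need a restriction such as permuted blocks, and then the list is not simple. The text could mean blocks mislabelled as simple, or stratification described as blocking with a promise it cannot keep. A reader cannot tell which, so the scheme cannot be reproduced or reported accurately from the protocol.

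The second half follows from the first. The trial separates randomization by ED in order to control child-adult balance, but the analysis does not say whether ED is in the model. Under simple lists, leaving it out costs precision if 60-minute pain differs between children and adults. Under balanced lists, leaving it out makes the test conservative. An unspecified term is also a choice that could be made after the data are seen.

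**Working it through.** **Inputs from the documents.** Difference 13 mm, SD 22 mm, alpha 0.05, power 80%, 45 per group (Data Analysis). Allocation of 1:1 is inferred from the equal group sizes, and the test is taken as two-sided.

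**Assumed inputs.** The documents give neither the number of children, *m*, nor the child-adult gap in mean 60-minute pain, *g*. I use *m* = 20, 30, 40 and *g* = 0 to 20 mm.

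**1. The plan's own figure.** n per group = 2(1.960 + 0.842)² × 22² / 13² = 44.96, so 45. This reproduces the stated size (normal-approximation power 80.04%; with the t distribution 79.2%).

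**2. Balance of children under simple lists.** The number of children in one arm is Binomial(*m*, 0.5), whether or not the list is separate. For *m* = 20, P(equal) = C(20,10)/2²⁰ = 184,756/1,048,576 = 17.6%.

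| Children | Exactly equal | 60:40 or worse |
|---|---|---|
| 20 | 17.6% | 50% |
| 30 | 14.4% | 36% |
| 40 | 12.5% | 27% |

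**3. Power at 60 minutes under simple lists.** The total SD is held at 22, including the gap, so the within-ED variance is 484 − *g*² × *p*(1 − *p*), with *p* = *m*/90. For *m* = 30 and *g* = 15 this is 484 − 225 × 2/9 = 434, an SD of 20.83. With ED in the model, the noncentrality is 13√W / SD(within) on 87 degrees of freedom. W is the sum over the two EDs of n₁n₀/(n₁ + n₀), where n₁ and n₀ are the numbers per arm in that ED. Without ED, the SD is 22 on 88 degrees of freedom. Both are averaged over all possible splits.

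Without ED, power is 78.7%. With ED:

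| Children | g = 0 | 5 | 10 | 15 | 20 mm |
|---|---|---|---|---|---|
| 20 | 78.2% | 78.6% | 79.7% | 81.5% | 84.1% |
| 30 | 78.2% | 78.7% | 80.1% | 82.5% | 85.8% |
| 40 | 78.2% | 78.8% | 80.3% | 83.0% | 86.7% |

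The term costs 0.5 points at no gap and breaks even near 5 mm. Simulated type I error without ED stays at 4.9% to 5.2%.

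**4. Level and power under exactly balanced lists, 30 children.** Balance removes the gap from the true variance of the difference, but an unadjusted test still uses the SD of 22. The level is then about 2[1 − Φ(1.96 × 22 / SD(within))]. For *g* = 15: 1.96 × 22/20.83 = 2.07, giving 3.8%. Simulation of 100,000 trials per setting gives:

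| Gap (mm) | Level without ED | Power without ED | Power with ED |
|---|---|---|---|
| 0 | – | 79.2% | 79.2% |
| 10 | 4.5% | 79.8% | 81.1% |
| 15 | 3.9% | 80.5% | 83.4% |
| 20 | 3.0% | 81.4% | 86.6% |

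At 15 mm the level without ED is 4.0% with 20 children and 3.8% with 40. With ED in the model it is 4.9% to 5.1%.

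**5. Change from baseline.** If the gap is constant over time it cancels from each patient's change. With 30 children and an assumed within-ED correlation of 0.5, simulated type I error is 4.9% to 5.1% with or without ED. Adding ED alters power by about −0.4 points under simple lists and 0.0 under balanced lists, at every gap from 0 to 20 mm.

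**The case against.** In experimental design, blocking can also mean randomizing separately within levels of a nuisance factor, and the word is attached to exactly that step. On this reading the text describes one simple list per ED, and only the promise of equality is too strong. That reading is fair and narrows the contradiction, but the promise still fails: separate simple lists do not have the property claimed for them. Nothing in the text rules out permuted blocks either.

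On the analysis, the plan is silent about ED and does not exclude it. The gap is part of a generally unspecified model, and an unadjusted analysis would be valid. The benefit also rests on assumptions. At 10 mm under simple lists the gain is only 1.0 to 1.6 points (79.7% to 80.3%, against 78.7%). A 20 mm gap is nearly one full SD, and the documents support no particular gap. The introduction states the aim in terms of the adult ED, so fewer than 20 children is possible, and the gain would then be smaller.

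Finally, the sample size sentence speaks of a difference in pain reduction. If change from baseline is the tested quantity and the gap is constant, ED gains nothing. That is a live reading, although Outcome Measures names the difference in means at 60 minutes as primary. All of this limits the weight of the point. It does not remove the inconsistency in Interventions or the low cost of naming the term.

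**Conclusion.** The concern holds. The failure of the balance guarantee under simple lists needs no assumption; only the probabilities depend on the assumed 20 to 40 children. The analysis does not specify the factor by which the trial randomizes.

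The statistical impact is modest. Validity is not threatened: type I error is about nominal under simple lists and below nominal under balanced lists. Across the settings examined, under simple lists, adding ED changes 60-minute power by between −0.5 points and +8.0 points (86.7% − 78.7%, with 40 children and a 20 mm gap). These figures depend on the assumed gap and number of children, and on the 60-minute level being the tested quantity. The point should be corrected, but it does not put the trial's conclusion at risk.

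**What to change.** 1. **Describe the list as it was actually made.** If it was simple, state that allocation is stratified by ED through separate lists, and delete "to ensure equal numbers of pediatric patients in both the experimental and control arms (blocking"). If it was blocked, delete the word simple and report the block scheme used.
2. **Prespecify ED in the primary comparison.** Suggested wording: *ED (adult or pediatric) will be a fixed factor in the model that gives the between-group difference in mean VAS at 60 minutes.*

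The cost is one reworded sentence, one model term and one degree of freedom. No new list and no change in sample size are needed. If children and adults do not differ at 60 minutes, the power cost is about 0.5 points under simple lists (78.7% to 78.2%) and none under balanced lists (79.2% either way).
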